Verification of Expert

Dear expert ,

My name is xxx, and I come from University Putra, Malaysia. My research topic is " Effect of 12-weeks resistance training in water combined with land on starting and turning performance of Chinese adolescent swimmer " You have a wealth of theoretical knowledge and long experience in adolescent swimming training. For now, we want you to validate whether my 12 weeks of resistance training intervention is reasonable? Your suggestion is very important to my research. I can promise, your suggestions only use me to perfect the experiment design and will not be used for any other purpose. All information you give will be kept confidential.

Thank you so much for being so helpful, and best wishes to you.

University Putra Malaysia

Supervisory Committee:

10 August 2021

Title: Effect of 12-Weeks Resistance Training in Water Combined with Land on Starting and Turning Performance of Chinese Adolescent Swimmer

Expert: _____

Specialized field: _____

1. Questionnaire information

This questionnaire adopts a 5-point scale, with 1-5 representing increased support (1= strongly agree, 2= agree, 3= no need, 4= disagree, 5= strongly disagree). Can you grade the training intervention? Please submit your comments in the "Suggestions for improvement" section. If there's anything else. You can add them and indicate the name. After reading, please score the following aspects and tick " ✓ " on the corresponding scoring scale. Finally, as we all know, you are a well-known expert in this field. I hope you can give me some advice. Your opinion is very important to me and will help me improve my intervention plan.

2. Executive Summary

Resistance training has been widely used in various sports and is a common practice aimed at improving competition performance, especially in swimming. Swimming performance is highly dependent on muscle strength, especially short distances. Water or land resistance training can improve the swimming performance, especially the swimming performance of 50 meters and 100 meters. Both type of training has their own strength and weakness. Hence, combining both methods strength may enhance swimmer performance. In addition, competitive swimming consists of different stages, namely start, clean swim, turn and finish. However, there is no literature on the influence of resistance training on starting and turning.

Through experimental design and quantitative research methods. In this experiment, the resistance training method of water combined with land was used to intervene the turning and starting of young people, and the traditional strength training was compared to find out a better training method. The experiment will use 12 weeks of resistance training to improve the swimmer's turn and start intervention. The experiment consisted of four groups, 20 boys and 20 girls in the experimental group and 20 boys and 20 girls in the control group. Compare the differences between the two groups. Divided into discussion groups and general teaching groups.

Two of the most significant differences, this experiment aims to provide a theoretical basis for improving the training methods of swimming, so that young swimmers can get better swimming performance, especially on the start and turn.

To evaluate the effectiveness of a 12-week water combined with land
resistance training intervention

Table 1. Intervention Plan-Same Characteristics

Content	1. Land Combined Water Resistance Exercises Group 2. Traditional Strength Training Group	Improvement suggestions
Athlete Qualification	Similar age groups : 11-12	
	Same training background (Three years of training)	
	No other resistance training was given during the experiment.	
Coach Qualification	From the same club	
	Same experience: Minimum more than 10 years	
	Physical education graduate	

Table 2. Different resistance loads and intervals in strength training (Fleck, 1997)

Loads	>13RM	11-13RM	8-10RM	5-7RM	<5RM
Intervals	<1min	1-2min	2-3min	3-5min	<5min

Table 3. Percentage of 1RM Repetition Scale (Santana, 2015)

Percentage of Repetitions Maximum (%1RM)	100%	95%	90%	85%	80%	75%	70%	65%	60%
Maximal Repetition	1	2	4	6	8	10	12	14	16

Table 4. Arms

Arms	Arm Description	picture	Improvement suggestions
Drag Umbrella ,	In the water, a small umbrella is attached to the athlete to increase resistance.		
Resistance Bands	On land, use a stretch rope to increase resistance.		
Hand Resistance.	In the water, increase resistance by increasing the area of the hand.		
Swiss Ball	On land, inflatable bouncy balls are used to increase strength.		

Medicine Ball,
	
On land, solid balls are used to increase strength.
		

Pulley Pull,
	
On land, pulleys are used to increase resistance.
		

Resistance Suit.
	
In the water, use swim shorts that increase resistance
		

Table 5. Intervention Plan Design – Must make sure you have land and water right?

Group	Experiment Group				Control Group				Improvement Suggestions
Week	1-3	3-6	6-9	9-12	1-3	3-6	6-9	9-12	
Strength training	Hand Resistance	Hand Resistance	Resistance Suit	Resistance Suit	Sit-Up	Sit-Up	Dumbbell	Dumbbell	
	Drag Umbrella	Drag Umbrella	Drag Umbrella	Drag Umbrella	Press-Up	Press-Up	Barbell	Barbell	
	Resistance Bands	Resistance Bands	Pulley Pull	Pulley Pulls	Deep Squat	Deep Squat Lift Heel	Stomach Up	Stomach Up	
	Swiss Ball	Swiss Ball	Medicine Ball	Medicine Ball	Lift Heel		Squat Up	Squat Up	
Swimming	1500m				1500m				
Frequency	3/week				3/week				
Warm Up	10 min				10 min				
Basic Training	50-60% 1RM 3 sets*15	60-70% 1RM 3 sets*15	70-80% 1RM 3 sets*15	80-90% 1RM 3 sets*15	50-60% 1RM 3 sets*15	60-70% 1RM 3 sets*15	70-80% 1RM 3 sets*15	80-90% 1RM 3 sets*15	
Interval	1min	3min	3min	5min	1min	3min	3min	5min	
Stretch	10min	12min	12min	15min	10min	12min	12min	15min	

*Idea: Based on (Fleck, 1997. Santana, 2015)

Table 6. Training Program (Warm Up)

Warm Up (10 min)	Improvement Suggestions

 ● Jogging (2 min) ● Aerobic Warm-Up (8min) 
 1. Neck Up and Down 2. Around The Shoulder 3. Arm Swings Backwards 4. Turn The Waist 5. Lunges Leg Press 6. Side Leg Press 7. Roll Your Knees 8. Turn The Ankle 9. Turn The Wrist 	

Table 7. Training Program(Stretch)

[figure not shown]
Stretch(10 -12min)	Improvement Suggestions

 ● Static Stretching 
 1. Arm Stretch 
 a) Forearm stretch b) Big arm stretch 2. Trunk 
 c) Chest stretch d) Abdomen drawing a) Stretching back 3. Leg 
 a) Leg before test b) Calf stretch 	

[figure not shown]
Forearm stretch

[figure not shown]
Big arm stretch

[figure not shown]
Chest stretch

[figure not shown]
Abdomen stretch

[figure not shown]
Stretching back

Stretching back

Thigh stretch

Thigh stretch

Calf stretch

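### Does the expert questionnaire's 1-5 scale, introduced in one direction and labelled in the other, call for a change to the plan?

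*Protocol*

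**What the plan says.** The protocol is built around a letter and questionnaire sent to experts in adolescent swimming training. Section 1 (Questionnaire information) asks "Can you grade the training intervention" and gives one scoring rule, a five-point scale described in a single sentence: "with 1-5 representing increased support (1= strongly agree, 2= agree, 3= no need, 4= disagree, 5= strongly disagree". The opening clause sets a direction, and the bracket that completes the sentence defines the codes. Experts are then told to put a tick "on the corresponding scoring scale" and to write comments under suggestions for improvement.

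The cover letter (Verification of Expert) limits what the replies are for: "your suggestions only use me to perfect the experiment design and will not be used for any other purpose". The rest of section 1 is to the same effect: the expert's opinion is meant to help improve the intervention plan.

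**The concern.** A rating scale needs one direction. Here the lead-in says that support rises with the number, while the labels put the strongest agreement at 1 and the strongest disagreement at 5. The conflict sits inside one sentence of running prose, so a broken table or a lost figure cannot explain it.

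The worry is easy to state. An expert who trusts the lead-in and ticks 5 for full approval would be recorded, under the labels, as rejecting the item outright. If some experts followed the lead-in and others the labels, their digits could not be compared. An intervention component could then be dropped or kept on the strength of a score read backwards.

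**Working it through.** There is no stated figure to reproduce. The check has three steps.

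**1. Set the two readings side by side.** The inputs are the two halves of the scoring sentence in section 1. On a 1-5 scale the reversed reading of a score x is 6 − x, and the distance between the two readings is |x − (6 − x)| = |2x − 6|.

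| Code x | Label | Reversed reading 6 − x | Distance |
|---|---|---|---|
| 1 | strong agreement | 5 | 4 |
| 2 | agreement | 4 | 2 |
| 3 | midpoint | 3 | 0 |
| 4 | disagreement | 2 | 2 |
| 5 | strong disagreement | 1 | 4 |

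So 4 of the 5 codes would have two opposite meanings, but only when the digit is separated from its label. With the label attached, each code has one meaning. This table therefore describes what a reversed scale is; it does not estimate harm.

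**2. Ask which half a reader would follow.** The labels name all five points one by one. The lead-in is a single general phrase that comes immediately before them. A reader who meets the phrase meets the definition of code 1 next. Labels attached to each point ordinarily define a scale, and the general phrase only describes it. Changing the lead-in to the opposite direction leaves the labelled meaning of every code as it is (0 of 5 altered). Reversing the labels would alter 4 of 5 (codes 1, 2, 4 and 5). The smaller correction points to a slip in the lead-in.

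**3. Follow the scores to where they are used.**

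- *Acceptance of the intervention:* the document gives no cut-off, no required level of agreement and no number of experts.
- *Summary:* no averaging or pooling rule is given. A mean m would become 6 − m under reversal, but no mean is called for.
- *Allocation:* the Executive Summary describes 20 boys and 20 girls in each of the experimental and control groups, with no reference to expert scores.
- *Outcomes and analysis:* starting and turning performance are the subject of the trial. The expert grades do not enter them.
- *Visible feedback:* Tables 1, 4, 5, 6 and 7 carry a column for written suggestions. A written comment does not depend on which end of a scale is high.

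The scoring grid that the tick instruction refers to does not appear in the text at hand. It may have been lost when the file was read, and nothing can be inferred from its absence. If the words are printed beside the numbers, a tick has only one meaning.

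**The case for a change.** The strongest case for acting is that this is the only scoring rule in the available text, that the experts are asked to score as well as comment, and that no comment is required for each score. A bare 5 from an expert who followed the lead-in would then be misread by 4 points, the full width of the scale, and nothing on the form need reveal it. The correction costs one word.

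Part of this stands. The contradiction is real, and the document never says which half governs. The rest depends on several conditions holding together: the expert disregards labels in the same sentence, the grid omits the words, the digit is read alone, and a decision turns on that digit. The document describes none of these. A low cost of correction does not turn a wording slip into a fault in the trial's design.

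The midpoint label is awkward English for neutrality. It conflicts with nothing else in the document and is a matter of wording preference.

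**Conclusion.** The sentence is wrong as written, and the error is clerical. Its reach ends at a questionnaire completed before the trial, whose stated purpose is to refine the intervention. Correcting the lead-in would change the meaning of 0 of 5 labelled codes. It would also change nothing in the comparison of groups, the outcomes or the conclusions. Anyone retyping the form can tidy the phrase; that is editing, not a change to the plan.

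This rests on two assumptions. First, experts and investigators read the scores by their labels, which the layout of the sentence makes likely but which the document does not confirm. Second, no unseen rule converts the scores into an acceptance decision; the protocol contains none. Whether any returned score was in fact misread cannot be told from the document.

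### Do the three descriptions of the groups leave the main comparison, or the role of sex in it, unsettled?

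*Protocol*

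**What the plan says.** Three consecutive sentences in the design paragraph (Protocol, section 2, Executive Summary) describe the groups.

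- The first gives the numbers: "The experiment consisted of four groups, 20 boys and 20 girls in the experimental group and 20 boys and 20 girls in the control group".
- The second gives the comparison: "Compare the differences between the two groups".
- The third reads: "Divided into discussion groups and general teaching groups".

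Just before these, the same paragraph states the purpose. Resistance training in water combined with land is used, and "the traditional strength training was compared to find out a better training method".

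Table 1 names the groups as "1. Land Combined Water Resistance Exercises Group 2. Traditional Strength Training Group". Table 5 sets out the training plan for one experiment group and one control group. Neither table is split by sex, and neither has a discussion or teaching arm.

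The protocol gives no statistical test, model, covariate, significance level, power or effect size.

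**The concern.** The number of groups appears to go from four to two, and then to a different pair altogether. A reader could draw three worries from this.

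- **Which comparison is primary.** If the four groups are the units of comparison, each contrast has 20 against 20 rather than 40 against 40. Testing all pairs would add a multiplicity problem.
- **Whether sex is ignored.** Boys and girls are recruited to fixed numbers in each arm, yet the comparison sentence does not mention sex. If sex is related to start and turn performance, a plain two-group test leaves that variation in the error term and gives an interval that is too wide.
- **Whether the arms are named correctly.** Discussion and general teaching are not interventions described anywhere else in the protocol.

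At stake would be the power of the main comparison, the false-positive rate, and a clear statement of what 80 swimmers are meant to show.

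**Working it through.** **Reading the sentences together**

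1. The sentence that says four groups also defines them: "20 boys and 20 girls in the experimental group and 20 boys and 20 girls in the control group". That is two named arms, each split by sex. The count is 4 x 20 = 80 swimmers, with 20 + 20 = 40 per arm, allocated 1:1. The figures agree with each other.
2. The sentence that follows refers to two groups. The pair just named is the experimental and the control group, and the purpose sentence, Table 1 and Table 5 all have exactly that pair. The natural reading is arm against arm, over all 80 swimmers.
3. The discussion and general teaching labels match nothing in the purpose sentence, Table 1 or Table 5. They are an error, but no procedure, schedule or table depends on them.
4. Table 4 is headed Arms but lists equipment, for example: "In the water, a small umbrella is attached to the athlete to increase resistance". This is another loose use of a word, with no effect on the design.

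**What each reading would mean for power**

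The protocol has no power figure to reproduce. Assume a two-sided 5% level, 80% power and effects in within-sex SD units. By the normal approximation, the detectable difference is (1.960 + 0.842) x sqrt(2/n), with n per group.

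| Comparison | Calculation | Detectable difference |
|---|---|---|
| Arm against arm, 40 v 40 | 2.802 x sqrt(2/40) | 0.63 SD |
| Within one sex, 20 v 20 | 2.802 x sqrt(2/20) | 0.89 SD (0.91 by the t-test) |
| Sex-by-training interaction, 20 per cell | 2.802 x sqrt(4/20) | 1.25 SD |

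All six pairwise t-tests on four groups of 20, unadjusted, give a simulated familywise error of 20.6% (20,000 runs). Of those six pairs, two compare the arms within a sex, two compare boys with girls within an arm, and two differ in both arm and sex. The protocol plans none of these sets of tests.

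**What leaving sex out would cost**

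Let boys and girls differ by s within-sex SDs. No value is given, so s is an assumption. With equal numbers of each sex in an arm, the pooled SD is sqrt(1 + s²/4). The power column uses this SD for both the true and the estimated standard error, at a true difference of 0.63 SD.

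| s | Pooled SD | Power |
|---|---|---|
| 0 | 1.000 | 80% |
| 0.5 | 1.031 | 78% |
| 1.0 | 1.118 | 71% |
| 1.5 | 1.250 | 61% |

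This slightly overstates the loss. With fixed 20/20 numbers, sex adds nothing to the true variability of the arm difference. Only the estimated standard error is too large. Power is then about Phi(2.802 - 1.960 x pooled SD):

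- s = 0.5: Phi(2.802 - 2.020) = 78%
- s = 1.0: Phi(2.802 - 2.191) = 73%

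The true type I error falls below the nominal 5%, to about 4.3% and 2.9%. The test is conservative. The estimated difference between arms is not biased by sex, because each arm has the same mix.

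**The case for a change.** The best case for acting is that the stray sentence is wrong on its face. It is not a PDF artefact or a redaction, and it is not something left to an analysis plan. The document goes to outside experts who are asked to judge the intervention, so a false description of the arms could mislead them. The choice between two arms and four cells is also design content, and two analysts could in principle read the paragraph differently: at a true difference of 0.63 SD, power is 80% with 40 v 40 but about 50% with 20 v 20.

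Some of this stands. The discussion and teaching labels are an error, and the four-then-two wording is loose. The rest does not carry far. An expert who reads on meets the correct arms in Table 1 and their full content in Table 5. The 20 v 20 reading needs the words four groups to override their own definition, the next sentence and both tables. The complaint about sex is inferred from silence: a comparison of two arms with sex as a factor is still a comparison of two groups. If the differences to be compared are changes from before to after training, a baseline gap between boys and girls would cancel, and only a sex difference in change would remain in the error term.

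**Conclusion.** No change to the plan follows. The protocol has one design: two training arms of 40, each with 20 boys and 20 girls, compared with each other. One sentence carries labels that belong to no part of this trial. That is a clerical slip, and removing it would alter nothing that is done, measured or concluded.

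Using sex as a model factor would be sensible, and it is a step analysts commonly take when groups are balanced by sex. The protocol does not rule it out, and a statistical analysis plan that is not shown may already provide for it. If it were left out, the cost would be precision only: about 2 to 9 points of power for a sex difference of 0.5 to 1.0 SD, or 2 to 7 points when the fixed 20/20 numbers are taken into account. There would be no bias and no excess of false positives. These figures rest on an assumed two-sided 5% level, 80% power, a true difference of 0.63 SD and the assumed sex difference. At 1.5 SD the loss would be larger, to about 61% power by the simpler formula.

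The 0.91 SD and 20.6% figures describe analyses that the protocol does not propose, so they do not count against it.

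### Do the shared weeks 3, 6 and 9 in Table 5 leave the training schedule in need of correction?

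*Protocol*

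**What the plan says.** Table 5 of the Protocol (Intervention Plan Design) sets out four phases for each group. Its Week row reads "Week 1-3 3-6 6-9 9-12 1-3 3-6 6-9 9-12": four labels for the experimental group, then the same four for the control group.

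The rows beneath give the content of each phase:

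- Load, sets and repetitions: "50-60% 1RM 3 sets*15 60-70% 1RM 3 sets*15 70-80% 1RM 3 sets*15 80-90% 1RM 3 sets*15".
- Rest, the same sequence in both groups: "Interval 1min 3min 3min 5min 1min 3min 3min 5min".
- Stretching: "Stretch 10min 12min 12min 15min", repeated for the control group.
- Exercises, which change between the second and third phases. The first exercise row is "Hand Resistance Hand Resistance Resistance Suit Resistance Suit Sit-Up Sit-Up Dumbbell Dumbbell".
- Session rate: "Frequency 3/week" in each group.

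The Executive Summary gives the length: "The experiment will use 12 weeks of resistance training to improve the swimmer's turn and start intervention". No other text assigns weeks 3, 6 and 9 to a phase.

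**The concern.** Each phase label after the first opens with the number that closed the one before it. Read literally, weeks 3, 6 and 9 each belong to two columns, and in every one of those weeks the columns disagree on at least one row. A coach looking up week 3 finds two rest intervals and two stretch times. In week 6 the coach finds two exercise lists.

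Two things would be at stake. First, a session delivered in a shared week could not be checked against a single prescription, and the amount of each phase would not be fixed. Second, if the two groups settled the overlap differently, the schedule would differ between them in a way the design does not intend. Table 5 is the only place where exercises, load and rest are tied to weeks, so nothing elsewhere in the document settles the matter.

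**Working it through.** **Inputs.** Labels 1-3, 3-6, 6-9 and 9-12 in both groups, and 3 sessions a week (Table 5). Programme length 12 weeks (Executive Summary).

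**Extent of the overlap.** Total sessions = 12 × 3 = 36. Shared weeks are 3, 6 and 9, so 3 × 3 = 9 sessions, and 9/36 = 25%.

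**Programme length.** Three ways of counting the labels:

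- Every label inclusive: 3 + 4 + 4 + 4 = 15 weeks, because three weeks are counted twice.
- Labels as differences between time points: 2 + 3 + 3 + 3 = 11 weeks, because the first label opens at 1 rather than 0.
- First label from the start of week 1 to the end of week 3, and each later label from the end of its first number to the end of its second: 3 + 3 + 3 + 3 = 12 weeks.

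The distinct weeks named are 1 to 12, with none missing. The labels are therefore compatible with the stated 12 weeks, and no stated total is wrong.

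**What differs in each shared week, in both groups.**

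| Week | Load bands (% 1RM) | Interval (min) | Stretch (min) | Exercises |
|---|---|---|---|---|
| 3 | 50-60 and 60-70 (share 60) | 1 and 3 | 10 and 12 | same |
| 6 | 60-70 and 70-80 (share 70) | 3 and 3 | 12 and 12 | 3 of 4 change (experimental), 4 of 4 change (control) |
| 9 | 70-80 and 80-90 (share 80) | 3 and 5 | 12 and 15 | same |

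The control count reads the merged second-phase entry as two separate exercises. Interval and stretch differ in 2 × 3 = 6 of 36 sessions, and exercises in 1 × 3 = 3 of 36. Frequency, warm-up, swimming distance, and sets and repetitions are the same in every column.

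**Sessions per phase.** Let a, b and c be the number of sessions in weeks 3, 6 and 9 held before the phase changes, each from 0 to 3.

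- Phase 1: 6 + a, from 6 to 9.
- Phase 2: (3 − a) + 6 + b, from 6 to 12.
- Phase 3: (3 − b) + 6 + c, from 6 to 12.
- Phase 4: (3 − c) + 9, from 9 to 12.
- Sum: 6 + 3 + 6 + 3 + 6 + 3 + 9 = 36 for every choice of a, b and c.
- Second exercise set (phases 3 and 4): 18 + (3 − b), from 18 to 21.

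With a, b and c equal to 1 or 2, each shared week holds sessions of both its phases, and all the printed labels are true at once.

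**Worst case between groups.** If one group changed phase as early as possible and the other as late as possible, interval and stretch would differ between them in 6 of 36 sessions (17%) and the second exercise set by 21 − 18 = 3 of 36 sessions (8%). Nothing in the document suggests this. The labels match cell for cell, and Table 1 has the coaches of both groups come from one club.

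**The case for a change.** The best argument for a change is that the overlap is printed in all eight cells, so it is not a fault of text extraction. Table 5 is also the sole training calendar, and a statistical analysis plan would not normally supply one. The document asks experts to judge whether the 12-week programme is reasonable, so they are judging a schedule with three unspecified changeover points. The reading that gives equal blocks has to be guessed, because the opening 1 is counted in while the opening 3, 6 and 9 are counted out. The edit would be small: one label per boundary per group, at most 3 × 2 = 6 labels.

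Most of this stands as description. The changeover points are not stated, and the columns do differ there.

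It does not stand that the two columns are irreconcilable. That holds only if each column must govern the whole of a shared week, and the document does not say so. Nor does it stand that a quarter of the programme is undefined: in each of the nine sessions most rows agree or overlap. A cheap edit is not a reason to require one when no comparison depends on it. The document is also still a consultation form, with columns inviting improvements, so a loose boundary label is the kind of detail that can be settled before training starts.

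**Conclusion.** The concern describes a real looseness, but no change to the plan follows. It is a labelling slip or an unstated changeover point affecting up to 9 of 36 sessions, with interval and stretch differing in 6 and exercises in 3. The phases are consecutive, their order is clear and the total stays at 36 sessions. Those delivering the training can run them in sequence without further instruction.

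The labels are identical in both groups, so the overlap favours neither and does not bias the comparison between them. That rests on one assumption: both groups settle the shared weeks in the same way. The document does not say so outright, but the matching labels and the common club make it the natural expectation. Tidying the row would alter no comparison, stated figure or conclusion. Which phase holds weeks 3, 6 and 9 is for the sponsor to reconcile, and no view is taken on it here.

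### Table 5 keeps 15 repetitions per set at 70-90% 1RM, where the protocol's own Table 3 allows at most 12 to 4, so the weeks 6-12 dose for pulley, dumbbell and barbell work cannot be delivered

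*Protocol*

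**What the plan says.** The Basic Training row of Table 5 (Intervention Plan Design) gives the dose for both arms in four phases. Load rises from 50-60% 1RM in weeks 1-3 to "60-70% 1RM 3 sets*15" in weeks 3-6, "70-80% 1RM 3 sets*15" in weeks 6-9 and "80-90% 1RM 3 sets*15" in weeks 9-12. The part after the load never changes, and the 15 has no unit.

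Table 3 sets out the most repetitions possible at each load from 100% down to 60% 1RM in steps of 5 points: "Maximal Repetition 1 2 4 6 8 10 12 14 16". The footnote to Table 5 says the plan rests on the two sources that head Tables 2 and 3.

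Table 2 pairs loads with rest: "Intervals <1min 1-2min 2-3min 3-5min <5min" for >13RM, 11-13RM, 8-10RM, 5-7RM and <5RM in turn. The rest row of Table 5 reads "Interval 1min 3min 3min 5min".

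In weeks 6-12 the listed exercises include "Pulley Pull Pulley Pulls" in the experimental arm. In the control arm they include dumbbell work and, in the row "Press-Up Press-Up Barbell Barbell", barbell work.

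**The concern.** A repetition-maximum scale states the most repetitions that can be completed at a given load. A plan that builds on such a scale and raises the load must lower the repetitions at some point. Table 5 does not. If 15 means repetitions, the prescription in the second half of the programme exceeds what the plan's own scale says is possible.

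The dose is the intervention under test. If it cannot be followed, each coach must decide whether to lighten the load or shorten the set, and the document gives no rule. What swimmers receive in weeks 6-12 is then undefined and cannot be reproduced. The written error is the same in both arms, so it does not itself bias the comparison. But the improvised cut touches one listed experimental exercise and two listed control exercises, so the delivered dose could drift apart by arm. That is a possible risk, not a shown bias, and the requirement in Table 1 for coaches of the same club and similar experience reduces it.

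**Working it through.** **Inputs.** Load ranges and 3 sets of 15 from Table 5; maximal repetitions from Table 3; rest intervals from Tables 2 and 5; frequency of 3 per week from Table 5. Assumption: 15 means repetitions per set.

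**Plan's own figure.** 3 × 15 = 45 repetitions per exercise per session, in every phase.

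**Check against Table 3.** Ratio = 15 / maximum. Three-set ceiling = 3 × maximum, which takes every set to the maximum. Shortfall = (45 − ceiling) / 45.

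| Load (%1RM) | Maximum per set | 15 / maximum | Three-set ceiling | Shortfall from 45 |
|---|---|---|---|---|
| 60 | 16 | 0.94 | 48 | none |
| 65 | 14 | 1.07 | 42 | 3 (7%) |
| 70 | 12 | 1.25 | 36 | 9 (20%) |
| 75 | 10 | 1.50 | 30 | 15 (33%) |
| 80 | 8 | 1.88 | 24 | 21 (47%) |
| 85 | 6 | 2.50 | 18 | 27 (60%) |
| 90 | 4 | 3.75 | 12 | 33 (73%) |

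**Highest load that allows 15.** Interpolating linearly between 60% (16) and 65% (14): 60 + 5 × (16 − 15) / (16 − 14) = 62.5% 1RM.

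**By phase.**
- Weeks 1-3 (50-60%): 15 is possible.
- Weeks 3-6 (60-70%): possible only up to about 62.5%. No exercise listed for this phase clearly has a 1RM unless, for example, the deep squat is loaded, so little rests on this phase.
- Weeks 6-9 (70-80%): impossible throughout; the maximum is 12 to 8.
- Weeks 9-12 (80-90%): impossible throughout; the maximum is 8 to 4.

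**Exercises affected in weeks 6-12.** Those with a clearly definable 1RM: pulley pull (1 of 4 experimental); dumbbell and barbell (2 of 4 control). Table 3 says nothing about a resistance suit, a drag umbrella or body-weight work.

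**Sessions affected.** Taking each phase as three weeks (an assumption, since weeks 3, 6 and 9 each appear in two phases): 6 × 3 = 18 of 12 × 3 = 36.

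**Which entry looks out of date.** By Table 3, 10RM = 75%, 8RM = 80%, 7RM = 82.5% and 5RM = 87.5% (the last two interpolated). A 15-repetition load is >13RM, for which Table 2 gives <1 min rest. Table 5 instead gives 3 min in weeks 6-9, which fits 8-10RM (75-80%), and 5 min in weeks 9-12, the top of the 3-5 min range for 5-7RM (82.5-87.5%). That suggests the load and rest were raised and the repetition count was left behind. The 3 min in weeks 3-6 is longer than Table 2 gives for 12-16RM (at most 2 min), so this inference uses weeks 6-12 only.

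**The case against.** The strongest reply is that the contradiction is conditional. The 15 has no unit, and the same cell also governs the drag umbrella and resistance suit, where seconds or metres are conceivable. Under such a unit this conflict disappears and only a missing unit remains. That stands as a condition. Repetitions is nonetheless the natural reading next to a count of sets and a %1RM load, in a plan that reproduces a repetition-maximum scale.

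The shortfalls also apply per exercise, not per session. If all four listed exercises are done as 3 sets of 15 (an assumption; 4 × 45 = 180 repetitions), the experimental arm with one affected exercise loses 9/180 to 21/180 (5% to 12%) in weeks 6-9 and 21/180 to 33/180 (12% to 18%) in weeks 9-12. The control arm with two loses 18/180 to 42/180 (10% to 23%) and then 42/180 to 66/180 (23% to 37%). This is fair context.

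The rest-interval inference is only partly supported. At 70% the load is 12RM, for which Table 2 gives 1-2 min, not 3. The range 80-90% is 8RM to 4RM, so 5 min fits only its middle. Rest therefore hints at which entry to change but does not prove it. The contradiction does not depend on it.

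Last, the athletes are 11-12 years old, and the document does not discuss whether three sets at the maximum for 80-90% 1RM suit them. That is a reason to treat Table 3 as a ceiling and to consider the lower-load option seriously. It does not rescue 15 repetitions at those loads.

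**Conclusion.** Wrong as written, and it should be fixed. If 15 means repetitions, no load in weeks 6-12 satisfies both Table 5 and Table 3. The prescription is 1.25 to 1.88 times the possible maximum at 70-80% 1RM and 1.88 to 3.75 times at 80-90%. For pulley, dumbbell and barbell work, the best achievable volume at the stated load is 20% to 47% below plan in weeks 6-9 and 47% to 73% below in weeks 9-12.

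This rests on the repetitions reading, on Table 3 as the plan's own standard, and on limiting the claim to exercises with a clear 1RM. The three-set ceilings are generous, since they assume the maximum is reached in every set. The consequence is a dose that cannot be delivered or reproduced as written; a difference between arms is not shown.

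**What to change.** **Preferred.** Keep the rising load and cap repetitions per set at the Table 3 maximum for the load used: 16 to 12 at 60-70% (15 only up to about 62.5%), 12 to 8 at 70-80%, and 8 to 4 at 80-90%. If one count per phase is wanted, 12, 8 and 4 are allowed across the whole load range of phases 2, 3 and 4.

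**Alternative.** Keep 15 repetitions, hold the load at or below about 62.5% 1RM, and reset the rest to the <1 min that Table 2 gives for >13RM.

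Either way, write the unit in the row, say that the rule applies to exercises with a definable 1RM, and apply it identically in both arms.

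**Cost.** One table row (plus the rest row under the alternative), with no extra participants or procedures. The preferred option lowers planned volume for these exercises: 36, 24 and 12 repetitions per session instead of 45 in phases 2, 3 and 4 with one count per phase. The alternative gives up the load progression. Neither defines the dose for exercises without a 1RM.
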